8.7 Enrollment

When a patient and the principal investigator or authorized designee have personally signed and dated the Patient Informed Consent Form, the patient is considered a subject enrolled in the study. The date the subject signed the Patient Informed Consent Form and data protection authorization must be documented in the subject's medical records.

8.8 Baseline

The Baseline visit can be a standalone visit or can be performed on the same day of LINQ™ Insertion prior to the LINQ™ Insertion procedure.

The following information is required to be collected at the baseline visit:

- Patient Informed Consent Form
- Inclusion/Exclusion Criteria assessment (including pregnancy test if the subject is of child bearing potential)
- Medical History including most recent EF (if available in the last 6 months) and previous heart failure events in the last 6 months.
- Demographics
- Physical exam
- Medications
- Laboratory results: BNP, eGFR, Blood Urea Nitrogen (BUN), Serum Creatinine, Sodium (Na), Potassium (K), Hemoglobin (Hb), Hematocrit (Hct), Troponin
- Any healthcare utilizations
- Study deviations

8.9 Insertion

Within 30 working days of the baseline assessment, the Reveal LINQ™ device will be inserted in the subject. The insertion procedure will be performed in accordance with the Medtronic Reveal LINQ™ implant instructions. After the Reveal LINQ™ device is inserted, the LINQ™ HF investigational RAMware will be downloaded to the device via the 2090 programmer. Use of the recommended implant locations is located in Figure 8 below. Physicians should follow the implant manuals when performing the Reveal LINQ™ implant.

[figure not shown]

Figure 8: Recommended Insertion Locations

The following information is required to be collected at the insertion visit:

- Final system configuration
- Insertion procedure information
- LINQ™ HF Investigational RAMware download
- [REDACTED]
- Device interrogation (media/USB)
- Any Reveal LINQ™ system and procedure-related adverse events
- Any healthcare utilizations
- Any device deficiencies or study deviations

8.9.1 Programming Recommendations

Once the LINQ™ device is inserted into the subject, the physician is recommended to choose "AF management." This will automatically program the device to the nominal settings for the different detectors.

8.10 Scheduled Follow-up visits

After receiving notice of successful LINQ™ insertion, Medtronic will provide the target dates and windows for each visit to the implanting center. Should a subject miss a visit or the visit fall outside the pre-specified window, a study deviation must be reported and the original follow-up schedule maintained for subsequent visits.

Data analyses include follow-up visits, regardless of whether the visit occurs within the window. Therefore, a late visit is preferred over a missed visit but must be accompanied by a deviation. Follow-up visit windows are listed in Table 7 and are based on days post-insertion.

Table 8: Post-Insertion Follow-up Windows

Study Follow-up Visit	Window (Calculated days post-procedure attempt)		
	Window Start (# of days)	Target (# of days)	Window End (# of days)
1 month	30	30	37
6 month	163	183	203
12 month	345	365	385

The following information is required to be collected at the **1 Month** scheduled follow-up visits:

- Physical exam including temperature
- Symptoms review
- Medications
- NYHA assessment
- 6 Minute Hall Walk test
- [REDACTED]

- Device interrogation (media/USB)
- Any Reveal LINQ™ system and procedure-related adverse events
- Any healthcare utilizations
- Any device deficiencies or study deviations

The following information is required to be collected at the **6 Month and 12 Month** scheduled follow-up visits:

- Physical exam including temperature
- Symptoms review
- Medications
- NYHA assessment
- 6 Minute Hall Walk test (*DR220 Holter recommended to be used at 6 Month Visit Only during the 6 Minute Hall Walk test*)
- [REDACTED]
- Laboratory results: BNP, eGFR, Blood Urea Nitrogen (BUN), Serum Creatinine, Sodium (Na), Potassium (K), Hemoglobin (Hb), Hematocrit (Hct), Troponin
- Device interrogation (media/USB)
- Any Reveal LINQ™ system and procedure-related adverse events
- Any healthcare utilizations
- Any device deficiencies or study deviations

8.11 Device Transmission/ HCU Monthly Call (Start within Month 1)

There will be a Monthly Device Transmission eCRF to be completed starting within the first month from insertion. This visit will be conducted to ensure the subject manually transmitted the device data (see section 8.12 below). In addition, a HCU assessment will be completed in cases where the subject is contacted. Subjects should be contacted regularly (recommended at least every 3 months) regardless of manual transmission status to ensure complete and timely reporting of HCUs. Follow-up windows will vary based on the timing of the most recent device interrogation/transmission and will be provided by Medtronic as needed.

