2 SYNOPSIS

TITLE

Reveal LINQ™ Heart Failure (HF) Clinical Study

PURPOSE

The LINQ™ HF study is a Non-Significant Risk Investigational Device Exemption (IDE) study. The study is utilizing the Reveal LINQ™ device with an investigational LINQ™ HF RAMware download. [REDACTED]

The purpose of the LINQ™ HF study is to characterize Reveal LINQ™ derived data from patients with heart failure by assessing the relationship between changes in LINQ™ derived data and other physiologic parameters with subsequent acute decompensated heart failure (ADHF) events. The study will also collect information regarding HF related clinical events during the same period.

DESIGN

The study is a prospective, non-randomized, multi-center, observational, pre-market clinical study. The study is expected to be conducted at up to 30 centers in the United States. Up to 300 subjects will be enrolled to achieve approximately 40 heart failure events (no more than two per subject will contribute to the cumulative total). Study subjects will be followed for up to 3 years post-insertion or until official study closure defined as when Medtronic and/or regulatory requirements have been satisfied per the Clinical Investigation Plan and/or by a decision by Medtronic or regulatory authority, whichever occurs first. The expected study duration is approximately 4 years representing 1.5 years of enrollments and 2.5 years of follow-up.

MEDICAL DEVICE

Table 4: System Component Information

Model Number	Component	Manufacturer	Investigational or Market-released
LNQ11	Reveal LINQ™ Insertable Cardiac Monitor	Medtronic	Market-Released*
LNQ11	Incision Tool	Medtronic	Market-Released
LNQ11	Insertion Tool	Medtronic	Market-Released
SW026	2090 Programmer	Medtronic	Market-Released*
Not Applicable	Reveal LINQ™ RAMware titled: LINQ HF Research System, Rev 1.0, and subsequent versions as they are released**	Medtronic	Investigational
PA96000	Patient Assistant	Medtronic	Market-Released
24950	MyCareLink® Home Monitor	Medtronic	Market-Released
DR220	Holter	NorthEast Monitoring, Inc.	Market-Released

*The LINQ™ device and the 2090 programmer are market-released, but once the investigational LINQ™ HF RAMware is downloaded into the devices, they are considered investigational.

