A patient will be considered enrolled in the study once they sign and date the patient informed consent (PIC). The subjects will be followed via 1, 6 and 12 month in-office visits as well as monthly device transmission/healthcare utilization (HCU) calls. Study subjects will be followed for up to 3 years post-insertion or until official study closure defined as when Medtronic and/or regulatory requirements have been satisfied per the Clinical Investigation Plan and/or by a decision by Medtronic or regulatory authority, whichever occurs first. Table 4 below describes the required data collection and study procedures at the subject's visits.

Table 5: Data Collection and Study Procedure Requirements at Subject Visits

STUDY PROCEDURE	Baseline	LINQ Insertion	1 Mo Visit	6 Mo and 12 Mo Office Visit	Device Transmission/HCU Monthly Call	Study Exit
Patient Informed Consent	X					
Inclusion/Exclusion Assessment	X					
Medical History	X					
Demographics	X					
Physical Exam	X		X	X		
Medication Assessment	X		X	X		X
Laboratory results	X			X		
Symptoms and Temperature (via ear is recommended)			X	X		
Final system configuration		X				
Insertion procedure information		X				
LINQ™ HF RAMware download onto LINQ™ device		X				
██████████		X				
Device Data		X	X	X	X	X
NYHA functional classification assessment			X	X		
6 minute hall walk test			X	X		
Holter (DR220) with 6 Minute Hall Walk Test (Recommended)				X*		
██████████			X	X		
LINQ™ HF RAMware removal from LINQ™ device						X
Adverse Event	As Occurs					
Healthcare Utilization						
Device Deficiency						
System Modification						
Study Deviations						
Death						

*DR220 Holter is recommended at the 6 Month Visits.

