8.14 Healthcare Utilization

Cardiovascular-related Health Care Utilizations (HCUs) (including hypervolemia and hypovolemia) will be collected. This includes the following:

- Unscheduled clinic visit (including subject-initiated phone calls if the subject is experiencing CV-related symptoms)
- Scheduled clinic visit (if the subject is experiencing CV-related symptoms)
- Hospital outpatient clinic visit
- Urgent care visit
- Other outpatient utilization with overnight stay
- Emergency department visit
- Inpatient hospitalization

HCU information should be reported upon center awareness and assessed at all visits including the monthly telephone visits. If multiple HCUs occur within the same day, data from all HCUs can be captured on one eCRF.

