12.1 Risk Minimization

The potential risks associated with the LINQ™ HF investigational RAMware were identified, assessed, evaluated and effectively controlled. Any potential risks associated with this study are further minimized by selecting qualified investigators and training study personnel on the Clinical Investigation Plan.

In addition, investigators will be actively involved in the implantation and regular follow-up of the subjects implanted with the Reveal LINQ™ with investigational RAMware systems. At each office follow-up visit required per protocol (Table 6: Data collection and study procedure requirements at subject visits), the LINQ™ device will be interrogated, device data collected to verify appropriate device function and patient's health assessed for any adverse events.

Medtronic is further minimizing the possibility of risks by: performing required laboratory and pre-clinical testing prior to the clinical study, implementing quality control measures into production processes, providing guidelines for subject selection and evaluation, and providing adequate instructions and labeling.

Table 14: Potential Risks and Risk Minimization

Potential Risk	Minimization
ICM Pocket Infection from implant/explant procedure or over duration of implant	
 Industry standard sterilization and procedural processes will be followed to minimize the risk of infection Wound check following implant, per site's practice
Allergic reaction or ICM Rejection following implant procedure	
 Assessment of subjects to ensure no allergic or rejection reaction to materials used in incision/insertion tools, Reveal LINQ™ ICM exterior or incision closure method Wound check following implant, per site's practice Close monitoring with follow-up appointments Investigator discretion to remove ICM and report study deviation Use of biocompatible materials in the Incision/ Insertion Tools and Reveal LINQ™ ICM exterior patient-contacting surfaces

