- Patient has severe valvular heart disease as defined by hemodynamically significant valve stenosis and/or prosthetic heart valve
- Patient has existing IPG, ICD, CRT-D or CRT-P device
- Patient has severe renal impairment (eGFR <25mL/min)

Subjects will have in-office visits at 1 month post-insertion, as well as 6 and 12 months post-insertion. These in-office visits will include NYHA assessment, 6 minute hall walk, [REDACTED], [REDACTED], physical exam, medication assessment, and collection of symptoms and temperature. Blood tests will be performed at the 6 and 12 month visits. Following the 12 month visit, there will be no further required in-office visit until the exit visit in which the RAMware is removed from the device. In addition to in-office visits, subjects will perform monthly manual CareLink transmissions. [REDACTED]

This document is electronically controlled. Printed copies are considered uncontrolled.

Confidential

6. Determination of Sample Size

There are no sample size requirements as this is an observational study. However, 40 ADHF events with LINQ device data available for the most recent 30 days prior to the event will be collected; up to two events per subject may be used in the analysis, and these events must be at least 90 days apart. While any ADHF event with the requisite device data that occurs prior to a subject's exit may be used in the analysis, the sample size was selected in order that data can be derived from an estimated 40 subjects with a ADHF event within 12 months. This provides a conservative estimate of the required number of subjects. The CHAMPION study provides a 12 month KM estimate of HF hospitalization of 30% for Class III subjects¹. To be conservative, it is assumed 25% of enrolled subjects will have at least one ADHF event within 12 months. If the estimate is used as a binomial proportion, a sample size of 300 subjects would accrue ≥ 40 subjects with event within 12 months with $> 99\%$ probability. If the proportion of subjects with ADHF event is lower than 25%, the probability of at least 40 subjects with at least one ADHF event is $> 88\%$ if the underlying proportion of subjects with event is $\geq 16\%$. The projected enrollment number of 300 may be readjusted if the frequency of ADHF events is higher or lower than anticipated.

7. Statistical Methods

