For subjects who have multiple ADHF events, plots may be produced with time on the x-axis, and daily average value for a particular feature on the y-axis, with periods in which the ADHF events occurred noted as well. The graph may have the following format. Because the lack of required follow-up visits beyond 12 months may result in ADHF events going unreported, a summary of the plot of a single subject's readings over time should include a marker at 12 months to denote the point at which required follow-up visits ended for this subject.

This document is electronically controlled. Printed copies are considered uncontrolled.

Confidential

Subjects who do not experience an ADHF event included in the analysis will have their daily data averaged across these subjects for each day post-insertion and plotted as reference for comparison with the data summaries described above.

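### Between the 12-month visit and study exit, no scheduled contact lists a question on device adverse events or device deficiencies, so late events managed without explant or repositioning rest on spontaneous reporting or recall at exit

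*Combined protocol and SAP*

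**What the plan says.** **Length of follow-up.** The protocol synopsis says "Study subjects will be followed for up to 3 years post-insertion or until official study closure", and gives the overall timeline as "The expected study duration is approximately 4 years representing 1.5 years of enrollments and 2.5 years of follow-up".

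**Contacts.** The synopsis also says "The subjects will be followed via 1, 6 and 12 month in-office visits as well as monthly device transmission/healthcare utilization (HCU) calls". SAP section 5 adds: "Following the 12 month visit, there will be no further required in-office visit until the exit visit".

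**Content of the periodic contact.** Protocol 8.11 has it check the monthly manual transmission. Then: "In addition, a HCU assessment will be completed in cases where the subject is contacted". Speaking to the subject at least every 3 months is a recommendation, given for the sake of HCU reporting. Protocol 8.14, in contrast, says: "HCU information should be reported upon center awareness and assessed at all visits including the monthly telephone visits". HCU collection in 8.14 is restricted to cardiovascular-related use.

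**Where device adverse events are listed.** System- and procedure-related adverse events, with device deficiencies, are required items in 8.9 (insertion), 8.10 (months 1, 6 and 12), 8.15 (system modification) and 8.16 (exit). Section 11.2.1 collects such adverse events from consent for the whole study. Tables 5 and 7 put adverse events, deficiencies and HCUs in one as-occurs block.

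**Risk section.** Section 12.1 says adverse events are assessed at each office visit the protocol requires. Its Table 14 names "ICM Pocket Infection from implant/explant procedure or over duration of implant" as a risk.

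**SAP.** Section 7.10 summarises device adverse events from consent to exit as counts and percentages of subjects, with a listing that gives onset date and days post-procedure. Section 7.9.4 warns about late ADHF events ("Because the lack of required follow-up visits beyond 12 months may result in ADHF events going unreported"). Section 7.10 has no matching caution.

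**The concern.** The protocol recognises a device risk that lasts as long as the implant, but the office-visit check that 12.1 describes stops at month 12 and resumes only at exit. The one recurring contact in between has a script without the device-safety items, and its HCU review would not bring up a skin or pocket problem handled as a non-cardiovascular matter. A subject who transmits reliably need not be spoken to at all.

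Two things are at stake. First, the percentages in SAP 7.10 cover consent to exit, so a reader would take them as equally well ascertained throughout; minor late events could be undercounted with nothing in the table to say so. Second, such events may come to the site's attention later than they need to. The sponsor has already accepted the general argument: HCUs are also reported as they occur, yet 8.11 recommends regular contact to make their reporting complete, and SAP 7.9.4 expects ADHF events to be missed once required visits end.

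**Working it through.** The documents give no figure for adverse-event ascertainment, so there is none to reproduce. The check has two parts.

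**1. Which scheduled contacts carry the device adverse-event and deficiency items**

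| Contact | Protocol section | Items listed? |
|---|---|---|
| Insertion | 8.9 | yes |
| Months 1, 6, 12 | 8.10 | yes |
| Periodic transmission/HCU contact | 8.11 | no |
| System modification, at any time | 8.15 | yes |
| Study exit | 8.16 | yes |

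After month 12, a subject without a system modification is next asked at exit.

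**2. How much follow-up lies in that stretch**

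*One subject.* Inputs: last scheduled visit at month 12 (day 365, window 345 to 385, Table 8); follow-up T of at most 36 months, or 30 months on the 2.5-year description. Share = (T − 12)/T.

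- T = 36: 24/36 = 66.7%. With a maximum of 1,095 days, the window gives (1,095 − 385)/1,095 = 64.8% to (1,095 − 345)/1,095 = 68.5%.
- T = 30: 18/30 = 60.0%.
- Longest interval between scheduled questions: 1,095 − 365 = 730 days, against 183 − 30 = 153 and 365 − 183 = 182 days in year 1.

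*Person-time, by closure date.* Assumptions: 300 subjects entering uniformly over 18 months, no dropout, 36-month cap, study closing c months after first enrolment. A subject entering at month e has follow-up f = min(36, c − e), or 0 if e is after c. Share = sum of max(f − 12, 0) divided by sum of f.

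| Closure c (months) | Share after month 12 |
|---|---|
| 48 | 65.7% |
| 42 | 62.5% |
| 36 | 55.6% |
| 30 | 42.9% |
| 24 | 26.7% |

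For c = 48, mean follow-up is (12 × 36 + 6 × 33)/18 = 35 months, and (35 − 12)/35 = 65.7%.

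*Early closure.* SAP 7.8 allows follow-up to end once 40 qualifying events are in hand. Take a constant hazard, first events only, counted from month 1 (the 30-day rule), and entry at 300/18 = 16.67 subjects per month.

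- Planned 25% at 12 months: h = −ln(0.75)/12 = 0.02397 per month. Expected events by c = 16 are 16.67 × [15 − (1 − exp(−15h))/h] = 16.67 × 2.40 = 40.0. Share after month 12 = (4²/2)/(16²/2) = 8/128 = 6.3%.
- Lower rate of 16%: h = −ln(0.84)/12 = 0.01453. Expected events by c = 20 are 16.67 × 2.39 = 39.8. Share = (8²/2)/((20² − 2²)/2) = 32/198 = 16.2%.

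The share of person-time is therefore roughly 6% to 66%, depending on when the study closes.

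**The case against.** **Collection never stops.** Adverse events and deficiencies are reported as they occur from consent onward, and exit asks once more. This stands: it is a gap in scheduled asking, not in collection. It is not a full answer, because HCUs are also reported as they occur and 8.11 still recommends regular contact for them. Recall at exit is also unavailable for many subjects lost to follow-up.

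**Serious device problems surface anyway.** Any explant or repositioning triggers the system modification form with adverse-event, deficiency and interrogation items (8.15). Deaths go on a form that records relatedness (11.5.1). Monthly transmissions continue, and a missed one requires a deviation unless an interrogation file is supplied. All of this stands. What remains is events handled without touching the device; 8.12 describes no question about pocket or skin.

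**The size depends on closure.** Correct. The 6% end is close to a lower bound, because closure at 40 events is optional, and missing device data or adjudication would delay the count. Second events per subject, ignored above, would bring it forward.

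**The monthly eCRF may already prompt for adverse events.** Possible: Appendix A places the forms under separate cover and they could not be checked. The protocol text does not require the prompt.

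**Late events are identifiable.** The SAP 7.10 listing shows days post-procedure. That helps for reported events only.

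**The 8.11 and 8.14 wordings are compatible.** Section 8.14 can be read as covering only calls that take place. The text leaves this open, so it is a wording point and not a proven contradiction.

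**Conclusion.** The point holds in a limited form. From month 12 to exit, at most 24 of 36 months for a subject, no scheduled contact in the protocol lists a device adverse-event or deficiency question. Late events managed without explant or repositioning depend on spontaneous reporting or recall at exit. The person-time affected is roughly 6% to 66%, under uniform accrual, no dropout and, at the lower end, a constant event rate with closure at the 40th event.

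Three stronger readings might be inferred and are not supported:

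- That device adverse events are asked about only at months 1, 6 and 12. They are also required at insertion, system modification and exit.
- That premature explants would be undercounted. Section 8.15 captures them whenever they occur.
- That two thirds of follow-up is typically uncovered. That is the maximum, and event-driven closure could make it far smaller.

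The documents give no rate for late device events, so the number likely to be missed cannot be estimated. This is a cheap improvement in safety ascertainment; the primary objective is unaffected.

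**What to change.** 1. **Protocol 8.11.** Whenever the subject is contacted, have the Monthly Device Transmission eCRF record system- and procedure-related adverse events and device deficiencies, using the items already listed from insertion onward. If the form already has them, only the protocol text needs aligning.
2. **Protocol 8.11 and 8.14.** Reconcile the two: one makes HCU assessment conditional on contact that is recommended every 3 months, the other refers to assessment at monthly telephone visits. Making 3-monthly contact compulsory is a workload decision for the sponsor, and this point does not depend on it. Tables 5 and 7 need no new mark, since adverse events and HCUs both sit in the as-occurs block.
3. **SAP 7.10.** Add the caution that 7.9.4 gives for ADHF events: ascertainment is reduced after month 12. Optionally, show adverse events by onset before and after month 12, each with its follow-up time.

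Cost: a protocol wording change, one or two form fields, slightly longer calls, and possibly a slightly higher reported adverse-event rate.

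### The plan does not fix how often subjects are asked about healthcare utilizations between visits, and after month 12 time that nobody asked about is counted as event-free

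*Combined protocol and SAP*

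**What the plan says.** Three places describe monthly contact about HCUs. The protocol synopsis has subjects followed by "monthly device transmission/healthcare utilization (HCU) calls" in addition to the office visits. Protocol 8.14 wants HCUs "assessed at all visits including the monthly telephone visits". The heading of protocol 8.11 names a monthly HCU call.

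The operative text of 8.11 is weaker. The required item is a monthly form on device transmission: "This visit will be conducted to ensure the subject manually transmitted the device data". On HCUs and contact it says that "a HCU assessment will be completed in cases where the subject is contacted. Subjects should be contacted regularly (recommended at least every 3 months", and this frequency applies "regardless of manual transmission status to ensure complete and timely reporting of HCUs".

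Other routes exist. HCUs are to be collected at the 1, 6 and 12 month visits (protocol 8.10), at a system modification (8.15) and at study exit (8.16), and reported once the center knows of them (8.14). After month 12 no office visit is required until exit (SAP section 5).

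A heart failure event is by definition a qualifying HCU (protocol 14.2.5, SAP 7.9.2). SAP 7.9.4 recognizes the late-phase problem: "Because the lack of required follow-up visits beyond 12 months may result in ADHF events going unreported". Its response is a 12-month marker on single-subject plots, which are themselves optional.

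**The concern.** An HCU that is never reported is an outcome that is never observed. Between fixed visits, a site cannot tell from the protocol whether it must ask monthly, should ask quarterly, or may ask only when it happens to speak to the subject. Enforcement is also uneven. A missed transmission calls for a deviation unless an interrogation file covers the period (8.12), whereas a missed HCU contact breaches only a recommendation in 8.11.

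Two analyses then treat silence as absence of events. SAP 7.9.4 averages the daily data of subjects with no included event over each day since insertion, as the comparison for the pre-event profiles. If one of those subjects had an unreported decompensation, the days leading up to it sit in the comparator. SAP 7.11 divides the HF-related HCUs in each month by all follow-up months in that interval, with no condition that anyone had asked.

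**Working it through.** **Inputs.** 300 subjects, a target of 40 subjects with an event within 12 months, and event proportions of 25% and 16% (protocol 14.2.4). Visit targets at days 30, 183 and 365 (protocol Table 8). Follow-up up to 3 years, taken as 1,095 days. Monthly intervals K = 1 to 30 of 30.44 days (SAP 7.11). A 14-day pre-event window (SAP 7.9.4) and 30 days of required pre-event data (SAP 7.4). The documents give no ascertainment rate, so the share *s* of events that is found is an assumption throughout.

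**1. The plan's own figure.** For X ~ Binomial(300, p), P(X ≥ 40) is above 0.9999 at p = 0.25 and 0.912 at p = 0.16. The protocol's figures of >99% and >91% reproduce. If only a share *s* of event subjects is found, p becomes s × p:

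| s | true p = 25% | true p = 16% |
|---|---|---|
| 1.0 | >0.999 | 0.912 |
| 0.9 | >0.999 | 0.724 |
| 0.8 | 0.999 | 0.417 |

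At the planned 25% the target is safe. At 16% it is not, but this calculation covers first events in year 1 only. Three HCU visits are fixed in that year, and the plan accepts later events and up to two per subject.

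**2. Gaps between fixed HCU questions.**
- Month 1 to 6: 183 − 30 = 153 days.
- Month 6 to 12: 365 − 183 = 182 days.
- Month 12 to exit: up to 1,095 − 365 = 730 days, about 24 months.

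Over 36 months, monthly calls would give about 36 contacts and the recommended minimum about 36 / 3 = 12. After insertion only four are fixed: months 1, 6, 12 and exit.

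**3. Monthly HF-related HCU rates.** The rate is the number of HCUs found divided by all follow-up months. If a share *s* of HCUs is found and every month stays in the denominator, the expected rate is s × the true rate. With s = 0.9 or 0.8 (assumed), it is 10% or 20% too low. Interval 12 ends at 12 × 30.44 = 365 days, so 18 of the 30 intervals lie after the last fixed visit before exit.

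**4. Reference average.** Take 25% × 300 = 75 event subjects and 225 without an event. Suppose 10% or 20% of the 75 go unreported, and count only their pre-event days over 365 days:
- 10%, 14 days each: 7.5 × 14 / (232.5 × 365) = 105 / 84,862.5 = 0.12% of reference subject-days.
- 20%, 30 days each: 15 × 30 / (240 × 365) = 450 / 87,600 = 0.51%.

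This borrows the 12-month proportion because the plan gives none for later follow-up. It shows the order of magnitude and is not an estimate.

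**The case against.** The best defense is that 8.11 is not the only way HCUs are found. They are collected at every office visit and at exit, and the investigators manage these subjects' heart failure (protocol 8.1), so many events will reach the center anyway. In year 1 an event between visits is therefore more likely to be reported late than lost. This stands, and it confines the main gap to the period after month 12. There the exit question helps, but incompletely: it may come up to two years after the event, no exit form is required after a death, and a subject lost to follow-up may not be reachable (8.16).

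A reader might infer more from 8.11 in three ways.

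- That the primary outcome as a whole is sought only when a subject happens to be contacted. This is true only of contact between fixed visits.
- That events are lost mainly in subjects with complete device data, because sites would phone those who failed to transmit. No passage says so. The recommendation is expressly independent of transmission status, and an office interrogation can replace a missed transmission (8.12).
- That the reference group is seriously contaminated or the 40-event target endangered. The working does not support either at the planned 25%. Counting affected subjects, when the harm lies in their pre-event days, would exaggerate the first.

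It is also fair to say that this is a descriptive feasibility study with no hypothesis, and that the sponsor has acknowledged the late-phase risk. But the 12-month marker protects neither the reference average nor the monthly rates.

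**Conclusion.** The point holds, with moderate confidence, as a contradiction about how the sole source of ADHF events is ascertained between fixed visits, and as a gap in ascertainment chiefly from month 12 to exit. The contradiction and the gap of up to 730 days come straight from the documents. The downward bias in the HF-related HCU rates follows wherever events go unreported while their follow-up months are counted. Its size equals the unreported share, which is unknown. The effect on the reference average is probably small, about 0.1% to 0.5% of subject-days if 10% to 20% of event subjects were missed and only 14 to 30 pre-event days each are counted. The change is worth making because it is cheap and protects the outcome itself.

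**What to change.** 1. Bring the synopsis and protocol 8.11 and 8.14 to one stated interval for HCU contact, no longer than the 3 months already recommended. Monthly would also reconcile them.
2. Make that contact required from insertion to exit, whether or not the subject has transmitted, with an HCU question each time.
3. Add to the existing Monthly Device Transmission eCRF the date through which HCU status was confirmed.
4. In SAP 7.9.4 and 7.11, count a subject's time as event-free only up to that date. In 7.11 apply the same cut-off to events and to follow-up months; otherwise an event learned of later would enter the numerator without its time. Reported ADHF events remain eligible for the primary analysis.

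The cost is protocol wording, one date field, one or two SAP sentences, and approval of the revision by the sponsor and each center's IRB (protocol 6.3). Sites must make, and report deviations for, calls the plan already recommends. At a 3-month interval this is at most about 12 × 300 = 3,600 contacts over 3 years, some of which coincide with office visits.
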